---

## SUMMARY OF CHANGES TABLE

DOCUMENT HISTORY	
Document	Date
CSP Version 3.0	17-Jul-2023
CSP Version 2.0	14-Jun-2023

### Overall Rationale for the Modification:

The protocol has been amended primarily to change the comparator from (active) AZD7442 (EVUSHIELD) to placebo. This change was initiated to bring the design of the local study in line with the recent changes in the Main Cohort of ongoing Phase I/III global study (SUPERNova, NCT05648110). Comparative evaluation with placebo is the most informative and appropriate option at the current stage of clinical development program.

A summary of changes is presented below. Where applicable, the changes were also applied to the synopsis.

### **Summary of Changes:**

## **List of Substantial Modifications**

Section Number and Name	Description of Change	Brief Rationale
Global change	The comparator has been changed from (active) AZD7442 (EVUSHIELD) to placebo. As placebo comparator will be given as a single injection (whereas	Bringing the design of the local study in line with the recent changes in the Main Cohort of ongoing Phase I/III global study (SUPERNOVA,
1.1 Synopsis	AZD7442 previously required two injections) at each dosing occasion, the injection of matching placebo that was	CCI
4.1 Overall Design	part of the blinded AZD3152 administration has been removed	
4.3.2 Justification for Placebo	Added justification for use of placebo as a	
	comparator	Justification required due to the change of comparator

## List of Non-Substantial Modifications

Section Number and Name	Description of Change	Brief Rationale
Global change	The coding name “AZD7442” has been changed to current trade name “EVUSHIELD” throughout the document	Clarification of the text
Schedule of Activities	Remove of Medical history and demographics (including COVID-19 vaccine status and previous COVID-19 infection) assessment on Day 1	Clarification
8.2.4 Clinical Safety Laboratory Assessments	Minor change to language: pregnancy tests will be done locally (not specifically at a local laboratory)	Clarification, as urine tests may be performed at the clinic
1.3.3 Screening, Treatment, and Follow-up Activities – Main Cohort Participants	Added footnote to allow the screening troponin test to be performed on Day 1 (predose) and noted in the table that this assessment will be done using a local laboratory	Reflection of clinical practice
2.2.1 Severe Acute Respiratory Syndrome Coronavirus 2 Infection and Disease	Updated statistics for COVID-19 cases	Information brought up to date
2.2.2 AZD5156, AZD3152, and EVUSHIELD	Removed reference to “the ongoing pandemic”	Updated to reflect the decline in COVID-19 incidence
4.3 Justification for Dose	Removed sub-section “Justification for AZD7442 Dose”	Comparator is now placebo
6.5 Concomitant Therapy	In the table, the timeline for COVID-19 antivirals and EVUSHIELD has been reworded for clarity	Clarification
8.2.1 Physical Examinations	Each clinically significant abnormal finding from the time of study intervention administration (was previously following	Timeframe updated for consistency with AE collection period noted in Section 8.3.1

Section Number and Name	Description of Change	Brief Rationale
	randomization) should be reported as an AE	
9.4.3 Safety	Noted that the most recent version of MedDRA will only be used where possible	Contingency, as it may not always be possible to use the latest version

## 1 PROTOCOL SUMMARY

### 1.1 Synopsis

#### Protocol Title:

A Phase II Randomized, Double-blind Study to Evaluate the Safety, Neutralizing Activity and Efficacy of AZD3152 for Pre-exposure Prophylaxis of COVID-19 in Participants having an Increased Risk for Inadequate Response to Active Immunization

#### Rationale:

AZD3152, a single mAb, is being developed to have broad neutralizing activity across known SARS-CoV-2 variants of concern for pre-exposure prophylaxis of COVID-19.

This Phase II study will assess the safety and neutralizing activity of AZD3152 in adults with conditions increasing risk of inadequate protective immune response after vaccination and thus are at high risk of developing severe COVID-19.

Evaluation of safety and efficacy compared to placebo is a generally accepted approach in the early stages of clinical development of monoclonal antibodies (Decision of Council of the Eurasian Economic Commission November 3, 2016 №89 «Rules for conducting research on biological medicines in the Eurasian Economic Union»). This approach provides optimal comparative data for subsequent interpretation, is ethically justified and does not carry any additional risks in the conditions of a favourable change in the epidemic situation in the Russian Federation (in 2022, Rospotrebnadzor lifted restrictions imposed in connection with the pandemic). In addition, uneven inclusion in the study groups is planned – fewer participants will receive a placebo. All participants will be able to receive SARS-CoV-2 vaccines after the Day 29 assessments. The results of this study will provide clinical data on safety, neutralizing activity and efficacy of an innovation drug in the new region (the Russian Federation), which will be a mandated by Russian law additional data source for the AZD3152 marketing authorization in Russia and will help expand the available range of COVID-19 prophylaxis strategy in conditions of continually virus evolving.

#### Objectives and Endpoints

Objectives	Estimand Descriptions/Endpoints
Primary	
To evaluate the safety of AZD3152 compared with placebo	Population: Safety analysis set Endpoints: 

• Occurrence of AEs collected throughout the study

• Occurrence of SAEs, MAAEs, and AESIs collected throughout the study

 Intercurrent events: Treatment policy will be applied, i.e., all events collected will be included in the

	analysis regardless of the presence and timing of intercurrent events.  Summary measure: The number and proportion of subjects with AEs, SAEs, MAAEs, AESIs.
Secondary	
To compare the nAb responses to the SARS-CoV-2 emerging dominant variant(s) of concern circulating during the course of the study in serum following AZD3152 or placebo administration	Population: SARS-CoV-2 nAb analysis set  Endpoint: Titer for SARS-CoV-2 emerging dominant variant(s) nAbs  Intercurrent events: Participants who experience a protocol deviation that can interfere with an antibody response or violate adherence to the assigned dose, become infected, receive COVID-19 treatment or vaccination that can alter nAb levels will have data collected after the intercurrent event set to missing for analysis of this endpoint (i.e., while-on-treatment strategy is applied).  Summary measure: Geometric mean titer (GMT) and geometric mean fold rise (GMFRs) (from baseline value through Day 29 after the single IM dose) of SARS-CoV-2 nAbs.  Descriptive statistics for the log-transformed titer will include the number of participants, GMT and GMFR, corresponding gSD, 95% CI, minimum, and maximum and summarized by treatment arm.
To compare the incidence of symptomatic COVID-19 cases in participants receiving study intervention. (efficacy)	Population: Full analysis set  Endpoint: Incidence of a post-treatment symptomatic COVID-19 case (negative RT-PCR at baseline to positive RT-PCR or positive antigen test at any time up to 6 months AND symptoms specified in the modified WHO definition of symptomatic COVID-19).  Intercurrent events: Participants who become unblinded to treatment assignment and/or take other non-investigational product(s) for COVID-19 prevention, in both cases prior to having met the criteria for the COVID-19 endpoint, will have data collected after the intercurrent event set to missing for analysis of this endpoint (i.e., while-on-treatment strategy is applied).  Summary measure: incidence of a post-treatment symptomatic COVID-19 case.
Exploratory	
CCI	Population: CCI

## Overall Design

This is a Phase II study that will be conducted in approximately 116 participants to evaluate the safety, neutralizing activity and efficacy of AZD3152.

Participants will be randomized in a 3:1 ratio to receive AZD3152 (300 mg, 2 mL) or placebo (2 mL) administered IM in the anterolateral thigh.

Study intervention will be handled by an unblinded pharmacist (or designee, in accordance with institutional regulations) at the study site who will be independent of safety evaluations and other trial evaluations.

If, following study intervention administration, a subject develops COVID-19, according to the Provisional recommendations on the methods for prevention, diagnosis and treatment of novel coronavirus infection (COVID-19), issued by the Ministry of Health of the Russian Federation, version 17 dated December 14, 2022 (Provisional recommendations 2022) (s)he must call “122” to be visited by a healthcare professional who, among other procedures, will perform a COVID-19 test. Once a visit by a healthcare professional has been requested, the subject must notify the study doctor of the date symptoms occurred and the date a healthcare professional visit has been requested, as soon as possible. Also, once a test result is available, the participant must report within 3 days the date of test and its result to the Investigator. If the test result is positive, the Investigator (or his/her delegate, according to the local regulations and institution guidelines) will make telephone calls *every three days* to collect safety data until the subject informs about his/her recovery.

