## Number of Participants:

In total, approximately 87 participants will be exposed to a single dose of AZD3152 (300 mg, 2 mL) IM, and 29 participants will be exposed to a single dose of placebo (2 mL) IM.

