## 4 STUDY DESIGN

### 4.1 Overall Design

This is a Phase II study that will be conducted to evaluate the safety, neutralizing activity and efficacy of AZD3152. The study will enrol approximately 116 adults who have a reduced immune response due to a disease/condition affecting the immune system and who are at risk of developing an underdeveloped immune response to vaccination and developing severe forms of COVID-19.

Participants will be randomized 3:1 to receive AZD3152 (300 mg, 2 mL) or placebo (2 mL) administered IM in the anterolateral thigh on Day 1. A prerequisite for inclusion in this study is that participants have immunocompromised conditions, including comorbidities that may contribute to reduced immunity, which in turn increases their risk of progression to severe disease.

AZD3152 or placebo will be administered as a single IM injection in the anterolateral thigh.

Study intervention will be handled by an unblinded pharmacist (or designee, in accordance with local and institutional regulations) at the study site who will be independent of safety evaluations and other trial evaluations.

The study will be conducted at approximately 10 sites in the Russian Federation.

Adverse events, SAEs, MAAEs, and AESIs will be collected throughout the study. Immediate AEs will be collected for an 1-hour observation period after study intervention administration. The duration of each participant's involvement in the study will be approximately 6 months from when the study intervention is administered.

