### 5.1 Inclusion Criteria

Participants are eligible to be included in the study only if all of the following criteria apply:

1. Participant must be 18 years of age or older at the time of signing the informed consent.
2. Written informed consent obtained from the participant prior to performing any protocol-related procedures, including screening evaluations.
3. Negative rapid antigen test SARS-CoV-2 at Visit 1.
4. Weight  $\geq 45$  kg at Visit 1.
5. Adult participants at increased risk of progression to severe forms of disease due to immunosuppressive diseases/conditions (Furer et al 2020, Poland et al 2018, Wagner and Weinberger 2020, Zimmermann and Curtis 2019), having at least 1 of the following risk factors:
  - Obese, ie, BMI  $\geq 30$
  - Congestive heart failure
  - Chronic obstructive pulmonary disease
  - Chronic kidney disease, ie, GFR  $< 30$  mL/min/1.73 m^2 (Lamb et al 2013)
  - Intolerant of vaccine. Defined as previous history of severe adverse event or serious adverse event after receiving any approved vaccine.
  - Immunocompromised state (must satisfy at least 1 of the following risk factors at enrollment)
    - a) Have cancer (eg, active solid tumors and hematologic malignancies) except for adequately treated:
      - Non-melanoma skin cancer or lentigo maligna
      - Uterine cervical carcinoma in situ
      - Local prostate carcinoma
    - b) Have solid organ transplant or a hematopoietic stem cell transplant (within 2 years of transplantation, are taking immunosuppression therapy or who have chronic graft-versus-host disease)
    - c) Are actively taking immunosuppressive medicines (eg, are using corticosteroids [ie,  $\geq 20$  mg prednisone or equivalent per day when administered for  $\geq 2$  weeks], high-dose alkylating agents, antimetabolites, transplant-related immunosuppressive drugs, cancer chemotherapeutic agents classified as severely immunosuppressive [eg, Bruton's tyrosine kinase inhibitors], tumor-necrosis blockers, or other immunosuppressive or immunomodulatory biologic agents for rheumatic diseases)
    - d) Received chimeric antigen receptor T-cell therapy

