### **6.1 Study Intervention(s) Administered**

#### **6.1.1 Investigational Products**

ASTRAZENECA AB will supply LLC AstraZeneca Pharmaceuticals AZD3152, solution for intramuscular injection, at a dosage of 150 mg / ml, 2 ml in a vial, as investigational drug in a standard package "IN BULK".

Further secondary packaging, labelling and release of IMP, will be carried out on territory of the Russian Federation by Manufacturing site and by Sponsor, in accordance with applicable regulations.

Placebo **CCI** [REDACTED]

Participants will be randomized to receive AZD3152 or placebo (3:1 ratio). There is no cap for randomization in each group to be implemented on site level of each investigational product, because it will increase coverage of IMP for trial conduction. Details of these study interventions are presented in [Table 5](#) and are described below.

Each vial of AZD3152 contains colourless to slightly yellow, clear to opalescent solution for injection. Label-claim volume per vial is 2 ml.

A placebo **CCI** [REDACTED] is colourless, clear solution for injection. **CCI** [REDACTED]

AZD3152 or placebo will be administered as a single IM injection in the anterolateral thigh.

If a participant experiences an immediate hypersensitivity reaction after receipt of the IM injection, appropriate necessary treatment should be prescribed. For details on the treatment of anaphylactic reactions after study intervention IM injections see [Appendix E](#).

Study intervention will be handled by an unblinded pharmacist (or designee, in accordance with local and institutional regulations) at the study site who will be independent of safety evaluations and other trial evaluations.

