## **6.3 Measures to Minimise Bias: Randomization and Blinding**

### **6.3.1 Randomization**

The participants will be randomized to receive AZD3152 or placebo (3:1 ratio).

All participants will be centrally assigned to randomized study intervention using an IWRS. Before the study is initiated, IWRS access and instruction will be provided to each site. Study intervention will be administered at the Visit 1.

The IWRS will provide to the Investigator(s) or pharmacists the kit identification number to be allocated to the participant at the dispensing visit. Routines for this will be described in the IWRS user manual that will be provided to each center.

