4.1.5 Baseline Characteristics

4.1.5.1 Presentation

Following baseline characteristics will be summarized for all participants in the Safety Analysis Set:

- Weight (kg)
- Height (cm)
- Body mass index (BMI, kg/m²)
- Sufficient medical conditions:
 - Obese, (BMI \geq 30 kg/m²)
 - Congestive heart failure
 - Chronic obstructive pulmonary disease
 - Chronic kidney disease, (GFR < 30 mL/min/1.73 m²)

- Intolerant of vaccine
- Immunocompromised state
- Previous COVID-19 vaccinations:
 - Participants previously vaccinated
 - Brand of last COVID-19 vaccine
 - Number of prior COVID-19 vaccinations received
 - Whether any bivalent booster was received or not
- Age group:
 - <60 years
 - ≥60 years

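### Protocol 6.3.1 names no stratification factor and no adverse event table uses immunocompromised state: with 29 on placebo, a modest chance imbalance that is cheap to reduce

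*Protocol*

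**What the plan says.** **Allocation.** The protocol synopsis states: "Participants will be randomized in a 3:1 ratio to receive AZD3152 (300 mg, 2 mL) or placebo (2 mL". Section 6.3.1 repeats the ratio and adds: "All participants will be centrally assigned to randomized study intervention using an IWRS". It mentions no stratification factor, block scheme or minimization, and no text there is blacked out. Sections 4.1 and 6.1.1 supply none either. Section 6.1.1 says: "There is no cap for randomization in each group to be implemented on site level". On sites, section 4.1 says: "The study will be conducted at approximately 10 sites in the Russian Federation".

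**Arm sizes.** The synopsis plans about 87 participants on AZD3152 "and 29 participants will be exposed to a single dose of placebo (2 mL) IM".

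**Entry.** Criterion 5 in section 5.1 admits adults "having at least 1 of the following risk factors". The list is obesity (BMI of at least 30), congestive heart failure, COPD, chronic kidney disease with GFR below 30, vaccine intolerance, and "Immunocompromised state (must satisfy at least 1 of the following risk factors at enrollment". That last group covers cancer, transplant, immunosuppressive medicines, CAR-T therapy, B-cell depletion and primary immunodeficiency. The Schedule of Activities has eligibility verified at screening and again before dosing on Day 1, the day of randomization.

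**Analysis.** The primary objective is safety compared with placebo, summarized as the number and proportion of participants with AEs, SAEs, MAAEs and AESIs in each arm. Protocol 9.1 and SAP 3.3.4 make this descriptive, with no test. SAP 4.1.5.1 lists "Immunocompromised state" among the baseline characteristics. None of the AE outputs in SAP 4.2.1.3 is split by it or adjusted for it.

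**The concern.** The primary question is comparative, and the comparator arm is small. Someone with obesity alone and a transplant recipient on immunosuppression would be expected to have different rates of adverse events, serious events and medically attended events over six months, whichever injection they receive. If the placebo arm happens to draw more or fewer immunocompromised participants than its share, the crude proportions shift for a reason unrelated to AZD3152.

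With no test and no adjusted estimate, readers will judge the raw percentages. The baseline table can reveal an imbalance in this factor, but nothing pre-specified says how the comparison would then be read. Any response would be devised after the data had been seen. The factor is already settled before randomization, so the protection costs little.

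**Working it through.** **1. The plan's own figures.** 116 x 3/4 = 87 and 116 x 1/4 = 29, as stated. The plan needs 108 evaluable; 108/0.95 = 113.7, and the next multiple of 4 that covers it is 116. The event threshold behind the 108 is blacked out. If it is 2% (assumption), log(0.20)/log(0.98) = 79.7, so 80, then 81 to fit 3:1, and 81 + 27 = 108. The sample size therefore rests on seeing an event in the AZD3152 arm, not on a contrast between arms.

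**2. Chance imbalance in case mix.** The documents do not give the immunocompromised share, so I assume 30%, 50% and 70%: K = 35, 58 and 81 of 116. Under simple random allocation, the number X in the placebo arm is hypergeometric(116, K, 29). The difference in share is D = (K - X)/87 - X/29, and

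SD(D) = sqrt[29 x (K/116) x (1 - K/116) x 87/115] x (1/87 + 1/29).

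For K = 58: sqrt(29 x 0.25 x 87/115) = 2.342, and 2.342 x 0.04598 = 0.108.

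| Assumed share | SD of D | 10 points or more | 15 points or more | 20 points or more |
|---|---|---|---|---|
| 30% or 70% | 9.9 points | 35% | 10% | 3.5% |
| 50% | 10.8 points | 39% | 20% | 8.5% |

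A 58:58 split at a 50% share would give an SD of 9.3 points, so 3:1 allocation raises it by about 15%.

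**3. Effect on the crude AE difference.** Shift = imbalance x gap in risk between the two groups. Assume any-MAAE risks of 40% (immunocompromised) and 15% (not), a gap of 0.25.
- One SD: 9.9 x 0.25 = 2.5 points, up to 10.8 x 0.25 = 2.7 points.
- A 20-point imbalance: 20 x 0.25 = 5 points.
- With a gap as wide as 40 points and shares of 20-50%, the shift has an SD of 3.4-4.3 points and reaches 10 points in about 0.2-3% of trials.

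**4. Comparison with ordinary sampling error.** At a pooled risk of 27.5%, SE = sqrt[0.275 x 0.725 x (1/87 + 1/29)] = 9.6 points, a 95% half-width of about 19. At 35% the SE is 10.2 points.

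**5. What the factor can recover.** At a 50% share, the part of the variance due to the factor is 0.25 x (pa - pb)^2 / [pbar x (1 - pbar)].
- 40% v 15%: 0.0156/0.1994 = 7.8%; SE 9.6 to 9.2 points.
- 15% v 3%: 0.0036/0.0819 = 4.4%; SE 6.1 to 6.0 points.
- 60% v 40%: 0.01/0.25 = 4.0%; SE 10.7 to 10.5 points.

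**6. Balance after stratifying.** Simulating a central 3:1 list in blocks of 4 within one yes/no stratum (shares of 30% and 50%), the SD of D falls from 9.9-10.8 points to about 1.5-1.6, with a maximum of about 3.5.

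**The case against.** The case for leaving the plan alone is strong on size. Randomization without strata is unbiased, and chance imbalance is already part of the sampling uncertainty. The dominant limit is 29 placebo participants, which stratification does not change. The study is descriptive and exploratory, and its size was not set for a between-arm contrast. SAP 4.1.5.1 tabulates all six risk groups by arm, so an imbalance would be seen. All of this stands, and it limits the claim to a modest one.

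The remedy also has limits. The group without immunocompromise still mixes obesity with heart failure, COPD and severe kidney disease, and the other group runs from a daily steroid to CAR-T therapy. Balancing yes/no does not balance severity within either. Weighted estimates for rare events would leave few or no events per cell. These points argue for a lighter analysis change, not for none.

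Three stronger readings are tempting and not supported:
- A reader might infer that the arms could differ markedly in underlying AE risk. The figures above give 2-3 points per SD against an SE near 10.
- A reader might infer that an imbalance could not be told apart from a treatment effect. The baseline table would show one on this factor.
- A reader might infer that the trial is unstratified. The IWRS specification is not among the documents, so they show only that no factor is stated.

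**Conclusion.** The point holds as a cheap improvement, not as a flaw that undermines the primary comparison. No stratification factor is stated, and immunocompromised state, known before randomization and tabulated at baseline, is used in no AE output. The immunocompromised share can differ between arms with an SD of about 10 points, and by 20 points or more in about 3-9% of trials, if 30-70% are immunocompromised. With assumed risks of 40% v 15%, this moves the crude difference by about 2-3 points per SD, well below the sampling SE of roughly 10 points. The recoverable variance is about 4-8% under the risk pairs tried.

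The case mix and the risk gaps are assumptions, since the documents give neither. Several correlated risk factors together could shift risk more than this single factor does.

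**What to change.** **Protocol 6.3.1 and the IWRS specification.** Stratify the 3:1 list by immunocompromised state (criterion 5, yes/no), with permuted blocks in multiples of 4. If the list is already stratified, say so and name the factor. Use one factor only: about 10 sites crossed with several factors would give too many strata for 116 participants.

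**SAP 4.2.1.3.** Keep the crude number and proportion per arm as the primary summary. Add AE, SAE and MAAE summaries by immunocompromised state. Add a stratum-weighted (Mantel-Haenszel) difference for the overall any-AE, any-SAE and any-MAAE rates only. Leave the sparse AESI and SOC/PT tables crude.

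**If randomization has started,** keep the list and add only the analysis, as a dated SAP amendment.

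**Cost.** One IWRS field already known at eligibility, a few extra tables and a short SAP addition, with no extra participants or procedures. The stratum may be mis-entered at randomization, so it should be checked against the eCRF. The gain in precision is small.
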